Subjects with ANC less than $1.8 \times 10^9/L$ at screening will not be enrolled in the study. All individuals with ANC $< 1.8 \times 10^9/L$, occurring at 7 days after the first dose, will have additional blood draws for complete blood count to be repeated on a weekly basis until the neutropenia resolves ($ANC \geq 1.8 \times 10^9/L$). In case the ANC is less than $0.5 \times 10^9/L$ after 1st vaccination, the subject will be immediately discontinued from 2nd vaccination and will have the test repeated on a weekly basis until the neutropenia resolves.

- All subjects (after DSMB evaluation of safety data from the initial 18 subjects with recommendation to switch to local normal ranges published for neutrophils):

Subjects with neutropenia defined as ANC less than $1.0 \times 10^9/L$ at screening will not be enrolled in the study. All individuals with a neutropenia ($ANC < 1.0 \times 10^9/L$), occurring

at any time during the study 7 days after the first dose, will have additional blood draws for complete blood count to be repeated on a weekly basis until the neutropenia resolves ($ANC \geq 1.0 \times 10^9/L$). In case the ANC is less than $0.5 \times 10^9/L$ after 1st vaccination, the subject will be immediately discontinued from 2nd vaccination and will have the test repeated on a weekly basis until the neutropenia resolves.

For classification and grading of severity of neutropenia for the first subset of 18 subjects, the criteria of Common Terminology Criteria for Adverse Events (CTCAE) issued by US Department of Health and Human Services (version 4.3; 2010) will be adopted. In case DSMB endorses the use of local ranges of normality for the second subset of 54 subjects, the grading will be modified based on input from DSMB. All individuals with neutropenia either ongoing or with onset at visit 5 (or last study visit) will have additional blood draws for complete blood count to be repeated on a regular basis until the neutropenia resolves ($ANC \geq 1.0 \times 10^9/L$ or $ANC \geq 1.8 \times 10^9/L$, depending on recommendations given by DSMB after evaluation of safety data from the initial 18 subjects).

Finally, all cases of neutropenia, regardless of intensity, will be considered as Adverse Events of Special Interest (AESI) from a reporting perspective.

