3.10 End of Study

Most clinical trials intended to support the efficacy/immunogenicity and safety of an Investigational Product proceed to full completion of planned sample size accrual.

Evaluation of the primary and/or secondary immunogenicity/efficacy objectives requires the testing of biological samples from the study subjects, which can only be completed after all samples are collected. The last samples for the analysis of the primary and/or secondary objectives will be taken at visit 5. For the purpose of this protocol, end of study is defined as the completion of the testing of such biological samples, to be achieved no later than 8 months after collection of the last biological sample visit 5.

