5.5 Study Termination Visit

The study termination visit 5 will occur 28 days after 2nd vaccination. The termination visit may be a clinic visit or a home visit. The date of termination is the date of the last contact (clinic visit or home visit) in which the subject's health status was assessed or, in cases where the subject does not agree to any further safety follow-up, it is the date consent is withdrawn. This date should be recorded on the termination CRF page. For visit procedures to be performed for a subject whose planned study participation ends prematurely, please see [section 5.5.1, Early Termination Visit](#).

At the clinic visit, the following procedures will be performed:

- review of subject's medical records and source document designed to collect solicited AE,
- review of systems, interview of subject to collect unsolicited adverse events, medically attended adverse events, AEs leading to withdrawal, SAEs, AESIs, and new onset of chronic disease,
- interview of subject to collect concomitant medications/vaccinations,
- symptom-directed physical assessment including measurement of vital signs and a check of general appearance,
- Blood sampling for immunogenicity and safety laboratory assessment,
- Urine sample for urine dipstick/urinalysis and pregnancy testing.

All individuals with neutropenia either ongoing or with onset at visit 5 (last study visit) will have additional blood draws for complete blood count to be repeated on a regular basis until the neutropenia resolves (for classification of neutropenia during the trial, refer to [Section 3.7, Procedures Related To Neutropenia](#)). Laboratory results obtained after study termination will be maintained in subject medical records and not entered in the CRF.

When the clinical study report is completed, the investigators will share the summary results with the participating communities. Town hall and village meetings will be held to convey the information and to allow for questions and answers.

The site will complete the termination CRF page and this will mark the completion of the subject's participation in the study.

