5.5.1 Early Termination Visit

When a subject is withdrawn from treatment or withdraws from the study, the investigator will notify the Sponsor and, when possible, will perform the procedures listed below. The reason(s) for the early termination will be included in the subject's source documentation. Early Termination Visits include subjects who were randomized but not treated.

At the clinic visit or during the home visit, the following procedures will be performed (if the Early Termination Visit is a home visit, collect as much information as possible):

- review of subject's medical records, source document and Diary Card,

- review of systems, interview of subject to collect unsolicited adverse events, medically attended adverse events, AEs leading to withdrawal, SAEs, AESIs, and new onset of chronic disease,
- interview of subject to collect concomitant medications/vaccinations,
- symptom-directed physical assessment including measurement of vital signs and a check of general appearance,
- blood sampling for safety laboratory assessment (no blood for immunogenicity assessment should be obtained unless this is agreed in advance with the sponsor),
- urine sample for urine dipstick/urinalysis and pregnancy testing.

All individuals with neutropenia either ongoing or with onset at last study visit will have additional blood draws for complete blood count to be repeated on a regular basis until the neutropenia resolves (for classification of neutropenia during the trial, refer to [Section 3.7, Procedures Related To Neutropenia](#)). Laboratory results obtained after study termination will be maintained in subject medical records and not entered in the eCRF.

The site will complete the termination CRF page and this will mark the completion of the subject's participation in the study.

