7.1.4 Serious Adverse Events

A serious adverse event (SAE) is defined as any untoward medical occurrence that at any dose results in one or more of the following:

- Death.
- Is life-threatening (i.e., the subject was, in the opinion of the investigator, at immediate risk of death from the event as it occurred); it does not refer to an event which hypothetically might have caused death if it were more severe.
- Required or prolonged hospitalization.
- Persistent or significant disability/incapacity (i.e., the event causes a substantial disruption of a person's ability to conduct normal life functions).
- Congenital anomaly/or birth defect.
- An important and significant medical event that may not be immediately life threatening or resulting in death or hospitalization but, based upon appropriate medical judgment, may jeopardize the subject or may require intervention to prevent one of the other outcomes listed above.

Adverse events which do not fall into these categories are defined as non-serious.

It should be noted that a severe adverse event need not be serious in nature and that a serious adverse event need not, by definition, be severe.

Serious adverse events will be captured both on the Vaccines Serious Adverse Event (VSAE) form as well as on the AE CRF. All SAEs will be evaluated by the investigator for relationship of the event to study vaccine. SAEs that are judged to be possibly or probably related to the study vaccine should be reported to the Sponsor as related/suspected events.

The relationship of the study treatment to an SAE will be determined by the investigator based on the following definitions:

1. Related/suspected

The SAE is judged by the investigator to be possibly or probably related to the study vaccine on the AE CRF page (see [section 7.1.3, Evaluation of Adverse Events](#)).

2. Not Related

The SAE is not related if exposure to the study vaccine has not occurred, **or** the occurrence of the SAE is not reasonably related in time, **or** the SAE is considered unlikely to be related to use of the study vaccine, i.e., there are no facts (evidence) or arguments to suggest a causal relationship.

The relationship of the study vaccine to an SAE will be determined by the investigator.

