7.1.4.1 Adverse Events of Special Interest

Adverse events of special interest (AESIs) are predefined adverse events that will be specifically highlighted to the investigator and will be summarized separately at the end of the study. All AESIs occurring during the study will be categorized and reported as a SAE.

Reactive arthritis (ReA) will be collected and analyzed as an AESI for this study.

Reactive arthritis is defined as non-purulent joint inflammation that develops in response to an infection in another part of the body. Since the inflammation is triggered by a previous condition, it is termed “reactive”. Intestinal pathogens that have been associated with reactive arthritis include *Campylobacter*, *Salmonella*, *Yersinia*, *Clostridium difficile*, and *Shigella*. If reactive arthritis is caused by an auto immune response, there is at least a possibility that it could be initiated by vaccination of susceptible people with the 1790GAHB vaccine.

For diagnosis of ReA, imaging and aspiration are not required (unless clinically indicated).

Neutropenia, a decrease of circulating neutrophils below the lower limit of the range of normality, will be collected and analyzed as an AESI for this study. To this purpose, as specified in the study procedures, subjects in this trial will have multiple blood draws for monitoring potential episodes of post vaccination neutropenia. For additional information on neutropenia, please refer to Section 3.7, Procedures Related To Neutropenia

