7.1.5 Methods for Recording Adverse Events and Serious Adverse Events

Findings regarding Adverse Events must be reported on an Adverse Events CRF, as specified in [section 7.1.1, Solicited Adverse Events](#), and on the VSAE form, if applicable, which is part of the Investigator Site File. All findings in subjects experiencing AEs must be reported also in the subject's source document.

All SAEs which occur during the course of the study, whether considered to be associated with the study vaccination or not, must be reported **within 24 hours of the site becoming aware of the event** to GVGH or its designee. Specific instructions and contact details for collecting and reporting SAEs to GVGH will be provided to the investigator.

All SAEs are also to be documented on the Adverse Events CRF. Any medication or other therapeutic measures used to treat the AE will be recorded on the appropriate CRF(s) in addition to the outcome of the AE.

After receipt of the initial report, representatives of GVGH or its designee will contact the investigator if it is necessary to obtain further information for assessment of the event.

All SAEs must be reported by the investigator to his/her IRB or applicable regulatory authorities in accordance with institutional policy/regulatory requirements and adequate documentation of this notification must be provided to the Sponsor.

GVGH or its designee must also comply with the applicable regulatory requirement(s) related to the reporting of suspected unexpected serious adverse vaccine reactions (also known as SUSARs) to the regulatory authority(ies) and the IRB/EC. If a SUSAR or other safety signal relating to use of one of the study vaccines is reported to GVGH or its designee, the Sponsor will communicate the information to the investigator and the investigator will be responsible for submitting this information to the IRB and other relevant authorities.

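### Blood counts repeated after study termination to follow neutropenia are kept out of the CRF, so the database lacks the values that show when, and whether, these cases resolved

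*Protocol*

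**What the plan says.** Protocol 5.5 sets the follow-up: "All individuals with neutropenia either ongoing or with onset at visit 5 (last study visit) will have additional blood draws for complete blood count", repeated until the neutropenia resolves. The same paragraph adds: "Laboratory results obtained after study termination will be maintained in subject medical records and not entered in the CRF". Section 5.5.1 repeats both parts for early termination: "Laboratory results obtained after study termination will be maintained in subject medical records and not entered in the eCRF". In each section, completing the termination CRF page ends the subject's participation.

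Other current text treats the event and its data differently:

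- Protocol 3.7: "Finally, all cases of neutropenia, regardless of intensity, will be considered as Adverse Events of Special Interest (AESI) from a reporting perspective". The same section defines resolution by ANC alone, at or above 1.0 or 1.8 x 10^9/L depending on the DSMB's recommendation.
- Protocol 7.1.4.1: "All AESIs occurring during the study will be categorized and reported as a SAE".
- Protocol 7.1.4: "Serious adverse events will be captured both on the Vaccines Serious Adverse Event (VSAE) form as well as on the AE CRF".
- Protocol 7.1.5: treatment given for an AE "will be recorded on the appropriate CRF(s) in addition to the outcome of the AE".
- Protocol 7.1.3: AEs are followed until they resolve or are judged chronic or stable. The assessment of AEs still ongoing at the last visit goes in the medical chart.
- Protocol 3.5 and 7.1.7: safety laboratory results go in the source documents and the CRF.

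**The concern.** The protocol orders blood counts on subjects with an AESI and then keeps the results out of the study database. Protocol 1.1 and 3.7 describe the phase 1 neutropenia (two subjects at grade 3, six at grade 2) as transient and clinically asymptomatic. If cases here are also silent, symptoms cannot show recovery and the neutrophil count is the only evidence of it. Protocol 1.2 calls this trial the first step towards testing in children, so how long any neutropenia lasts is something readers of the report will want to check.

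The sentence was already in protocol version 1.0. Amendment 2 later made neutropenia an AESI and marked the case report form as needing no revision. The rule may simply not have been revisited then, but the documents do not say so.

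**Working it through.** No sample size or power figure bears on this point. The check traces what reaches the database for a case present at the last visit, and then how much follow-up precedes termination.

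**1. What is barred and what is not.** Sections 5.5 and 5.5.1 bar laboratory results obtained after termination. They do not bar the AE outcome or end date. Under 7.1.4.1, 7.1.4 and 7.1.5 the event is an SAE on the VSAE form and the AE CRF, with its outcome recorded. A resolved or unresolved entry is therefore possible.

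**2. What supports that entry.** Resolution under 3.7 is a count at or above a threshold. For a case that resolves after termination, that count is only in the medical records, so the CRF entry cannot be checked within the database. No section says how the AE page is updated once the termination page is complete.

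**3. How much follow-up is captured before termination.** ANC is scheduled after vaccination at Visits 2, 3, 4 and 5 (Time and Events Table). Visit 4 is V3+7 with window 0/+1, so day 7 or 8 after Visit 3. Visit 5 is V3+28 with window 0/+7, so day 28 to 35.

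- Shortest gap from Visit 4 to Visit 5: 28 - 8 = 20 days.
- Longest gap: 35 - 7 = 28 days.
- Weekly repeats (Protocol 5.4) strictly before Visit 5: 2 within 20 days (days 7 and 14) and 3 within 28 days (days 7, 14 and 21).

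| Neutropenia first found at | Repeat counts in the CRF before Visit 5 | Counts after Visit 5 |
|---|---|---|
| Visit 4, still present at Visit 5 | 2 to 3, if weekly repeats are done | not entered |
| Visit 5 | none; only the Visit 5 count itself | not entered |

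**4. Which outputs are touched.**

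- Primary endpoint (e) (Protocol 8.1.1.1) is the number and percentage of subjects with reactive arthritis or neutropenia. It counts occurrence and does not change.
- SAP 13.3 summarises unsolicited AEs by onset. It does not change.
- SAP 13.2 plans duration for solicited AEs only, so no planned duration summary of neutropenia is damaged.
- SAP 13.5 plans a listing of all laboratory results, by vaccine group, subject and relevant parameter, for anyone with a clinically significant value. For an affected subject whose ANC is judged clinically significant, it would stop at termination.

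**The case against.** The strongest reply is that the rules can coexist. One governs laboratory values after termination and the other governs the AE outcome, and a site can obey both. The event is followed to resolution under 7.1.3, its outcome goes on the CRF, and the sponsor can ask the investigator for more under 7.1.5. Counts up to and including Visit 5 are in the CRF, and no primary summary changes. All of this stands and limits the point. It does not supply the missing counts or a rule for updating the AE page.

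Several stronger readings are tempting, but the documents do not support them:

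- A reader might infer that resolution is lost altogether, or that these cases must be reported as unresolved. The route through the AE CRF and VSAE form remains open.
- A reader might infer that depth cannot be shown. The Visit 5 value and earlier values are recorded; only a later nadir would be missed.
- A reader might take the eight phase 1 subjects as a guide to how many are affected. Protocol 1.1 and 3.7 do not say that any of those cases began at, or lasted to, a last visit.
- A reader might infer that 5.5.1 cuts off capture for subjects taken off the second vaccination for a low count. Its opening words do cover withdrawal from treatment, but 3.9 encourages such subjects to stay until the scheduled termination visit.
- A reader might take the 8 months in 3.10 as time in which the CRF stays open. The wording, "to be achieved no later than 8 months after collection of the last biological sample visit 5", limits sample testing; no database-lock date is given.

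One further limit is fair: under 3.9, a subject who withdraws completely has no further study interventions, so any change must respect that.

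**Conclusion.** The point holds as a gap in data capture. For neutropenia ongoing or starting at the last visit, the post-termination counts that define and verify resolution, any later nadir and the ANC-based duration are absent from the database. The SAP 13.5 listing is cut short for affected subjects who qualify for it. The outcome of the event can still be recorded, and endpoint (e) is intact.

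The documents give no number of affected subjects and none can be derived. The exposure can be stated only by visit: no follow-up count for onset at Visit 5, and 20 to 28 days of follow-up for onset at Visit 4. This rests on visits falling within their windows and on weekly repeats being done as 5.4 requires. It is a cheap improvement: the blood is drawn anyway, and the change would let the trial's own data show whether an AESI was transient.

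**What to change.** 1. In Protocol 5.5 and 5.5.1, replace the sentence on post-termination laboratory results. Blood counts done to follow neutropenia, in subjects who have not withdrawn consent to further follow-up, should be entered in the CRF as unscheduled results until resolution or database lock.
2. State that the outcome and end date of the neutropenia are updated on the AE CRF after the termination page is completed, and reconcile this with 7.1.3, 7.1.4.1 and 7.1.5.
3. In SAP 13.5, include these counts in the listing of all laboratory results, by arm.

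The cost is a few extra entries and CRF pages that stay open longer for affected subjects. How much longer cannot be stated, because the documents give no database-lock date. No additional blood draws are needed, and no new statistical analysis is required.

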5.5.1 Early Termination Visit

When a subject is withdrawn from treatment or withdraws from the study, the investigator will notify the Sponsor and, when possible, will perform the procedures listed below. The reason(s) for the early termination will be included in the subject's source documentation. Early Termination Visits include subjects who were randomized but not treated.

At the clinic visit or during the home visit, the following procedures will be performed (if the Early Termination Visit is a home visit, collect as much information as possible):

- review of subject's medical records, source document and Diary Card,

- review of systems, interview of subject to collect unsolicited adverse events, medically attended adverse events, AEs leading to withdrawal, SAEs, AESIs, and new onset of chronic disease,
- interview of subject to collect concomitant medications/vaccinations,
- symptom-directed physical assessment including measurement of vital signs and a check of general appearance,
- blood sampling for safety laboratory assessment (no blood for immunogenicity assessment should be obtained unless this is agreed in advance with the sponsor),
- urine sample for urine dipstick/urinalysis and pregnancy testing.

All individuals with neutropenia either ongoing or with onset at last study visit will have additional blood draws for complete blood count to be repeated on a regular basis until the neutropenia resolves (for classification of neutropenia during the trial, refer to [Section 3.7, Procedures Related To Neutropenia](#)). Laboratory results obtained after study termination will be maintained in subject medical records and not entered in the eCRF.

The site will complete the termination CRF page and this will mark the completion of the subject's participation in the study.

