3.9 Premature Withdrawal from Study

Subjects may withdraw at any time, or be dropped from the study at the discretion of the investigator should any untoward effects occur and/or for safety reasons. In addition, a

subject may be withdrawn by the investigator or the Sponsor if he/she violates the study plan or for administrative reasons. The investigator or study coordinator must notify the Sponsor immediately when a subject has been withdrawn due to an adverse event.

The circumstances above are referred to as premature withdrawal from the study, and the reason for premature withdrawal should be clearly documented and detailed in the source documentation. The investigator should make every attempt to evaluate the subject's safety, including resolution of ongoing AEs, at the time of premature withdrawal. If a subject wants to withdraw from the study before all doses are administered or prior to the last planned study visit, the subject will be asked to be followed for safety for the duration of the study. When a subject withdraws, or is withdrawn, from the study, the procedures described in [section 5.5.1, Early Termination Visit](#) should be completed if possible.

The reasons for premature withdrawal from the study include: Adverse event, death, withdrawal of consent, lost to follow-up, administrative reason, and protocol deviation. These reasons are described in greater detail below.

Adverse Event

For any subject withdrawn from study participation prior to the planned Study Termination Visit, it is important to determine if an AE was associated with the reason for discontinuing the study. This AE must be identified on the AE CRF page by indicating "Withdrawn from study due to AE". Any ongoing AEs at the time of study withdrawal must be followed until resolution or stabilization.

Subjects who develop a serious adverse event (SAE) judged to be possibly or probably related to the study vaccine, including hypersensitivity reactions, should not receive subsequent vaccination.

Death

For any subject withdrawn from study participation due to death, this should be noted on the Study Termination CRF page and the associated SAE that led to the death must be reported.

Withdrawal of consent

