In studies that involve more than 1 consecutive dose of study vaccine, a separate event is **“withdrawal of study vaccination”**. This event may occur if subjects are expected to receive more than 1 consecutive dose of vaccine as part of study participation. The act of withholding additional study vaccinations is referred to as withdrawal of study vaccination. Subjects may be withdrawn from study vaccination for several reasons including but not limited to: AE related to earlier vaccinations, failure to meet inclusion or exclusion criteria for revaccination (see [section 4.0, Selection Of Study Population](#)), or pregnancy. **Subjects who are withdrawn from study vaccination should be encouraged to continue in the study for safety follow-up and other procedures as appropriate until the scheduled termination visit.** If the subject is withdrawn from

study vaccination(s) due to adverse event, this event must be linked to the withdrawal from vaccination on the AE CRF page

Protocol Deviation

A protocol deviation is any change, divergence, or departure from the study design or procedures of a study protocol. In general, subjects associated with protocol deviations may remain in the study unless continuation in the study jeopardizes the subject's health, safety, or rights.

Investigators will apply due diligence to avoid protocol deviations. Under no circumstances should the investigator contact GVGH or its agents, if any, monitoring the study to request approval of a protocol deviation, as no authorized deviations are permitted. If the investigator feels a change to the protocol would improve the conduct of the study this must be considered a protocol amendment, and unless such an amendment is agreed upon by GVGH and approved by the IRB/EC and health authorities it cannot be implemented.

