Any subject who becomes pregnant during the study, despite the protocol requirement for adequate contraception, will not receive further vaccination but should be encouraged to continue participating in the study for safety follow-up. The site must complete a paper Pregnancy Report CRF (initial report) as soon as possible after learning of pregnancy occurrence (see [section 7.1.6, Pregnancies](#) for further details). If the subject withdraws from the study for any of the above categories except death, the site will obtain permission from the subject to continue to remain in contact with her until the outcome of the pregnancy is known, even if the outcome is not known until after the subject reaches the end of follow-up period.

Refer to [section 3.6, Stopping/Pausing Guidelines](#) and to [section 3.7 Procedures related to neutropenia](#) for further details in case of neutropenia.

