7. ASSESSMENTS

7.1 Safety Assessment

The measures of safety used in this study are based on previous study data. They include a close vigilance for, and stringent reporting of selected local and systemic adverse events routinely monitored in vaccine studies as indicators of reactogenicity.

An adverse event (AE) is defined as any untoward medical occurrence in a subject or clinical investigation subject administered a pharmaceutical product at any dose that does not necessarily have to have a causal relationship with this treatment. Therefore, an AE can be any unfavorable and unintended sign (including an abnormal laboratory finding, for example), symptom, or disease temporally associated with the use of an investigational product, whether or not considered related to the investigational product. This definition includes intercurrent illnesses or injuries and exacerbation of pre-existing conditions.

The period of observation for AEs extends from the time the subject signs informed consent until he or she completes the specified safety follow-up period (28 days after each vaccination) or terminates the study early (whichever comes first). AEs occurring after the informed consent form is signed but prior to receiving study vaccine/product will be documented as an adverse event and recorded within source document. However, any AEs occurring prior to receipt of any study vaccine will be analyzed separately from “treatment emergent” AEs (AEs occurring after administration of the first study vaccine).

Adverse events are collected as either solicited or unsolicited adverse events. Solicited events are derived from organized data collection systems, such as Subject interview.

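### Section 5.5.1 ends participation for subjects who only stop vaccination, in conflict with Section 3.9; the conflict is minor, but literal use would cut SAE and AESI collection short

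*Protocol*

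**What the plan says.** All references are to the current protocol (version 4.0).

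- **Section 5.5.1, trigger.** "When a subject is withdrawn from treatment or withdraws from the study, the investigator will notify the Sponsor" and, when possible, carries out the Early Termination Visit procedures. The section adds that this visit also covers subjects who were randomized but not treated.
- **Section 5.5.1, consequence.** "The site will complete the termination CRF page and this will mark the completion of the" subject's participation. No exception is made for a subject who has only stopped vaccination. "Laboratory results obtained after study termination will be maintained in subject medical records and not entered in the eCRF".
- **Section 7.1.** Adverse events are observed until the subject "completes the specified safety follow-up period (28 days after each vaccination) or terminates the study early (whichever comes first".
- **Section 3.9, route to 5.5.1.** "When a subject withdraws, or is withdrawn, from the study, the procedures described in" Section 5.5.1 are to be completed where possible. The trigger here is leaving the study.
- **Section 3.9, vaccination only.** Withholding further doses is defined as an event separate from study withdrawal. In bold type: "Subjects who are withdrawn from study vaccination should be encouraged to continue in the study for safety follow-up" up to the planned termination visit. A subject who becomes pregnant "will not receive further vaccination but should be encouraged to continue participating in the study for safety follow-up".
- **Section 5.5.** Refers to 5.5.1 for subjects whose planned participation stops prematurely.
- **Section 3.1 and synopsis Table 2, footnote h.** SAEs and AESIs are to be collected throughout the study.

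**The concern.** One section closes out a subject whom another section wants kept in follow-up. The protocol foresees such subjects. Dose 2 is withheld for an ANC below 0.5 x 10^9/L after dose 1 (Section 3.7), for a related SAE or pregnancy (Section 3.9), and for failed re-eligibility (Sections 4.1 and 4.2). Section 5.5.1 is the procedural text a site would open in those cases.

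Safety is the primary objective. SAEs throughout the study and AESIs (reactive arthritis or neutropenia) are primary endpoints (d) and (e) in Section 8.1.1.1. The termination page affects the data because Section 7.1 stops AE observation at early termination. Subjects whose second dose is withheld for a related SAE or marked neutropenia are among those whose later safety record matters most.

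**Working it through.** **No design figure depends on this point.** The synopsis figures reproduce: 1 - 0.9^20 = 87.8% (stated 87%), and 20/0.85 = 23.5, rounded up to 24 per group. Neither changes.

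**Step 1: compare the texts.**

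| Text | Who is sent to 5.5.1 | What happens to a vaccination-only withdrawal |
|---|---|---|
| 5.5.1 | Both kinds of withdrawal | Termination page; participation ends |
| 3.9 | Study withdrawal | Encouraged to continue to the planned last visit |
| 5.5 | Participation that stops early | Not addressed |

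The conflict with 3.9 is direct. With 5.5 there is only a mismatch of scope.

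**Step 2: lost follow-up for one subject if 5.5.1 is applied literally.** Inputs are the Table 2 visits and windows:

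- V2 = V1+7 (0/+1)
- V3 = V1+28 (0/+7)
- V5 = V3+28 (0/+7)

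Nominal follow-up after dose 1 is 28 + 28 = 56 days. The maximum is 35 + 35 = 70.

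*Stopped at Visit 3*
- Observed: 28/56 = 50%. Over the windows this runs from 28/(28+35) = 44.4% to 35/(35+28) = 55.6%.
- Not observed: V5 - V3 = 28 days (up to 35).
- Dose-1 unsolicited-AE window (endpoint c): 28/28 days, complete.
- Dose-1 safety panels (Visits 2 and 3): 2/2.

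*Stopped at Visit 2*
- Observed: 7/56 = 12.5%. The range is 7/70 = 10.0% to 8/56 = 14.3%.
- Not observed: 56 - 7 = 49 days (56 - 8 = 48 to 70 - 7 = 63).
- Dose-1 unsolicited-AE window: 7/28 = 25% observed (8/28 = 28.6% with the +1 day), so 21 of 28 days are lost nominally.
- Dose-1 safety panels: 1/2; the Visit 3 panel is lost.

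**Step 3: what continues anyway.**
- Ongoing AEs are followed to resolution or stability (Sections 3.9 and 7.1.3).
- Neutropenia is followed to resolution (Sections 3.7 and 5.5.1). Its outcome is recorded because every AESI is reported as an SAE (Sections 7.1.4.1 and 7.1.5). Only serial counts taken between early termination and the planned Visit 5 could be missing from the eCRF.
- Pregnancies are followed (Section 7.1.6).
- SAEs considered caused by the vaccine are reported after follow-up ends (Section 7.1.5.1).

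What lapses is scheduled collection of new AESIs and of SAEs not attributed to the vaccine. After a Visit 2 stop, new unsolicited AEs in the rest of the dose-1 window are lost too.

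**Step 4: can the analysis recover it?** The SAP derives study duration (8.8) and tabulates withdrawals (9.1) and vaccinations (13.1). Shortened follow-up would be visible there, but events never collected would not.

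**The case against.** The strongest reply is that the protocol already states the right rule. Section 3.9 is specific and in bold. Section 5.5 dates termination from the last contact at which health was assessed, or from withdrawal of consent; a subject still attending visits has reached neither. Section 3.9 also asks subjects who want to leave the study to be followed for safety to its end, so it would be odd if someone who merely missed dose 2 received less. Harm therefore requires a site to follow one loose phrase against clear text elsewhere. This stands, and it is why the conflict is minor. It does not remove the conflict: 5.5.1 states an unqualified consequence for both triggers, and no rule says which section prevails.

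Four stronger readings are tempting, and the documents do not support them:

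- **All safety follow-up stops.** It does not; see Step 3.
- **Two of four post-vaccination panels are lost after a Visit 3 stop.** Sections 3.1 and 3.5 tie the Visit 4 and 5 panels to the second vaccination, and endpoint (b) is counted after each vaccination. Without dose 2 there is no post-dose-2 panel to lose. The same applies to the second 28-day unsolicited-AE window.
- **Section 5.5 contradicts 5.5.1.** It only gives 5.5.1 a narrower scope.
- **The Amendment 2 rationale means subjects with ANC below 0.5 x 10^9/L should leave the study.** That precaution is worded for future protocols. Current Section 3.7 stops only the second vaccination and continues weekly counts.

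**Conclusion.** The point holds as a minor internal conflict in the current text. Section 5.5.1 applies a participation-ending step to subjects whom Section 3.9 wants kept in follow-up, and its scope is wider than Section 5.5 gives it.

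Its size is per subject and conditional on literal use of 5.5.1: about 28 of 56 days of scheduled SAE and AESI collection lost at Visit 3, or about 49 of 56 at Visit 2. Those day counts assume that the subject would otherwise have attended through Visit 5, which 3.9 encourages but does not require. The documents give no number of subjects affected, so no trial-level effect can be stated.

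**What to change.** Replace the closing sentence of Section 5.5.1 with: *The termination CRF page is completed, and participation ends, only when a subject withdraws or is withdrawn from the study, or was randomized but not treated. Subjects withdrawn from study vaccination only are encouraged to continue the scheduled visits through Visit 5, timed from Visit 3; for them the termination page is completed at Visit 5, and laboratory results obtained before that visit are entered in the eCRF.*

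For the first sentence there are two acceptable options:

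- Delete *is withdrawn from treatment or*, and put Sponsor notification for vaccination withdrawal in Section 3.9. That section now says only that site staff "must notify the Sponsor immediately when a subject has been withdrawn due to an adverse event", so it needs a short addition.
- Keep the words, but state that for vaccination-only withdrawals they trigger notification and a safety assessment, not termination. This could add one assessment with blood and urine sampling when the decision falls between visits.

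The cost is one sentence replaced by two, a small edit to the first sentence or to 3.9, and a matching CRF completion instruction. The first option adds no visits beyond those 3.9 already encourages. Continuing remains the subject's choice, and the sample size and planned analyses are unchanged.
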